6.5.1. Renal Impairment

A reduced dose of 600 mg/day (200 mg in the morning and 400 mg in the evening) is recommended in study subjects with mild to severe renal impairment (creatinine clearance [CrCL] 15 to 89 mL/min estimated by Cockcroft-Gault using actual body weight).

6.6. Prior and Concomitant Medications

During the study, if the use of any concomitant treatment becomes necessary (e.g., for treatment of an AE), the treatment must be recorded on the source document and eCRF, including the reason for treatment, name of the drug, dosage, route, and date of administration. All medications including prescription, over-the-counter (OTC), herbal and other nutritional vitamins and/or supplements taken within 30 days of the Baseline visit will be recorded on the eCRF. Note that vaccinations for COVID-19 are to be recorded on the source document and captured on the eCRF under both the concomitant medications section and on the COVID-19 forms.

6.6.1. Analgesic Use

Analgesic use, both prescription and OTC, will be collected in the eCRF in the same manner as other concomitant medications.

6.7. Prohibited Therapies/Products

Subjects enrolled in studies with pexidartinib who are also receiving concomitant warfarin should have their anti-coagulation status carefully monitored, especially shortly after initiation of pexidartinib, for the potential need for adjustments in warfarin dosing. In particular, INR should be obtained just prior to initiation of pexidartinib, within 1 to 2 weeks after initiation, and periodically thereafter. Dose adjustments of warfarin should be made as medically indicated.

Although pexidartinib does not appear to inhibit CYP drug-metabolizing enzymes to an important extent, caution is warranted when administering pexidartinib to subjects taking drugs that are highly dependent on CYP for metabolism and have a narrow therapeutic index. It is not known whether systemic exposure to these medications will increase while subjects are receiving pexidartinib.

Of the 5 major CYP isoforms, 3A4 (BFC) may be involved in Phase 1 metabolism of pexidartinib, with possibly CYP1A2 playing a minor role. Concomitant use of strong CYP3A4 inhibitors ([Table 10.2](#)) and inducers should be administered with caution, in the event they alter the systemic exposure to pexidartinib. In general, strong inhibitors or inducers of CYP3A4 should be avoided unless clinically necessary. These include anticonvulsants, certain mycin antimicrobials, and antiretrovirals.

Restricted Therapies/Products

If concomitant use with a strong CYP3A inhibitor ([Table 10.2](#)) or UGT inhibitor cannot be avoided, reduce the pexidartinib dose according to the recommendations in [Table 6.5](#). If concomitant use of a strong CYP3A inhibitor or UGT inhibitor is discontinued, increase the pexidartinib dose (after 3 plasma half-lives of the strong CYP3A inhibitor or UGT inhibitor) to the dose that was used before starting the inhibitor.

Table 6.5: Recommended Dosage Reductions for Pexidartinib for Concomitant Use of Strong CYP3A Inhibitors or UGT Inhibitors

Planned Total Daily Dose	Modified Total Daily Dose	Administration of Modified Total Daily Dose
800 mg	400 mg	200 mg bid
600 mg	400 mg	200 mg bid
400 mg	200 mg	200 mg once daily

bid = twice per day; CYP = cytochrome P450; UGT = uridine 5'-diphospho-glucuronosyltransferase

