4.1.3. Dose Regimen

Pexidartinib will be provided as an oral, daily administration at the dosage level at the end of their prior study. Doses will be taken on an empty stomach (at least 1 hour before or 2 hours after a meal or snack), at approximately the same times of the day, and approximately 12-hours apart.

Note: Dose escalation of pexidartinib treatment is not permitted during the course of this study.

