6.1. Study Drug(s) Description

[Table 6.1](#) describes the formulation, dose, regimen, duration, packaging, and labeling of pexidartinib.

Table 6.1: Study Drug Dosing Information

Study Drug Name	Pexidartinib
Dosage Formulation	200 mg capsules
Dosage Level(s)	The dose level at end of prior study will serve as the starting dose level. Note: Dose escalation of pexidartinib treatment is not permitted during the course of this study.
Route of Administration	Oral
Dosing	Pexidartinib should be administered twice daily approximately 12 h apart on an empty stomach (at least 1 hour before or 2 hours after a meal or snack).
Duration	Daily until subject's end of study
Packaging	PLX3397-HCl 200 mg capsules are manufactured, packaged, and labeled according to Good Manufacturing Practices and Good Clinical Practices (GCP). Packaging will clearly display the name of product, storage condition, and other required information as applicable in accordance with local regulations.
Labeling	Packaging will be labeled as required per local regulatory requirement.

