6.5. Guidelines for Dose Modification

Reduction or interruption of the dose for toxicity may take place at any time according to the guidelines in [Table 6.3](#). Dose reduction/interruption guidelines for hematologic and non-hematologic treatment-related TEAEs are based on severity. Dose interruptions can be implemented at the discretion of the treating physician to manage intolerable or clinically significant toxicity. If a dose interruption is required, study assessments should be performed as scheduled, irrespective of the study treatment delay. Interruptions due to toxicity lasting >14 days require treatment discontinuation unless the Medical Monitor approves continuation.

The recommended dose reductions for AEs are provided in [Table 6.2](#).

Table 6.2: Recommended Dose Reductions for Pexidartinib for Adverse Reactions

Dose Reduction	New Total Daily Dose	Administration of Total Daily Dose
First	600 mg	200 mg in the morning and 400 mg in the evening
Second	400 mg	200 mg twice daily

Subjects unable to tolerate 200 mg orally twice daily will be discontinued. Once dose reduction takes place for toxicity, a dose re-escalation is not allowed.

The recommended dosage of pexidartinib for patients with mild to severe renal impairment (creatinine clearance [CrCL] 15 to 89 mL/min estimated by Cockcroft-Gault using actual body weight, [Section 10.3.1](#)) is 200 mg in the morning and 400 mg in the evening.

Dose-modification guidelines for treatment-emergent toxicities as well as guidelines for their management are presented in [Table 6.3](#). These parameters are only a guide and are not intended to supersede the clinical judgment of the treating physician. All adjustments should be communicated to the Sponsor's Medical Monitor or designee. Re-challenge with a reduced dose of pexidartinib may result in a recurrence of increased serum transaminases, bilirubin, or ALP. Investigators will ensure weekly liver monitoring tests for the first 8 weeks after re-challenge, then every 2 weeks for the next month, then every 3 months or more frequently as directed by the Investigator.

Additional information can be found in the *PL3397-A-U4003 Study Manual* and the *Pexidartinib IB*.

Table 6.3: Recommended Dosage Modifications for Pexidartinib for Adverse Reactions

Event	Severity	Pexidartinib Dosage Modifications
Hepatotoxicity		

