Detailed history focusing on medications and substances used: alcohol, change in medication dosages, new medications added, attention to use of acetaminophen, OTC medication use and recreational drug use. Check for change in diet or use of dietary supplements, with particular attention to dose and duration of any herbal product	Suspect medications will be discontinued or substituted for if possible
Detailed medical history and physical exam seeking new abnormalities	Evaluate abnormalities found

Evaluation*	Comments
Full serological evaluation for hepatitis A, B, C and E (IgG and IgM). Check for autoimmune hepatitis with serological laboratory studies	If viral hepatitis or autoimmune hepatitis suggested, have subject evaluated by hepatologist
Liver ultrasound performed to evaluate liver and biliary tree	Evaluate any abnormalities found
Check history for exposure to chemical agents	Remove chemical exposure and have subject seen by hepatologist
Obtain hepatology consult if liver function continues to rise beyond 14 days	Contact Medical Monitor

Ig = immunoglobulin; INR = international normalized ratio; OTC = over-the-counter.

*Cases are to be discussed with the Medical Monitor whenever investigational product is being held for liver function test abnormality.

All dose modifications (interruption, delay, reduction, and/or discontinuation) should be based on the worst preceding toxicity (National Cancer Institute-Common Terminology Criteria for Adverse Events [NCI-CTCAE] version 5.0) as shown in [Table 6.3](#). Dose increases are not permitted for pexidartinib. Dose modification decisions may be based on laboratory results.

Once the dose of pexidartinib has been reduced because of toxicity, all subsequent cycles should be administered at that lower dose level unless further dose reduction is required. More than 2 dose reductions are not allowed and if toxicity continues after 2 dose reductions, the subject will be withdrawn from the study treatment if further toxicity meeting the requirement for dose reduction occurs.

For Grade 3 or Grade 4 events, monitoring (including local laboratory tests when appropriate) should be performed frequently and at an interval no greater than 7 days until the AE is determined to be resolving.

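### Section 6.7 orders a dose increase when a strong CYP3A or UGT inhibitor stops, but Sections 4.1.3, 6.1 and 6.5 bar increases without an exception, and the 6.7 target ignores toxicity reductions

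*Combined protocol and SAP*

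**What the plan says.** **Reduction and restoration for inhibitors.** Section 6.7 (Restricted Therapies/Products) applies Table 6.5 when a strong CYP3A or UGT inhibitor is unavoidable. The table maps a "Planned Total Daily Dose" of 800, 600 or 400 mg to 400, 400 or 200 mg. When the inhibitor is discontinued, the site is to "increase the pexidartinib dose (after 3 plasma half-lives of the strong CYP3A inhibitor or UGT inhibitor", and the target is a return "to the dose that was used before starting the inhibitor".

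**General bans.** Section 4.1.3 states: "Dose escalation of pexidartinib treatment is not permitted during the course of this study". Table 6.1 repeats this in the dosage-level row, straight after "The dose level at end of prior study will serve as the starting dose level". Section 6.5, in the text after Table 6.4, states: "Dose increases are not permitted for pexidartinib".

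**Toxicity rules.** Section 6.5 adds: "Once dose reduction takes place for toxicity, a dose re-escalation is not allowed". After a toxicity reduction, "all subsequent cycles should be administered at that lower dose level" unless a further cut is needed.

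No cross-reference, exception or order of precedence links Section 6.7 with the other sections.

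**The concern.** Two instructions point in opposite directions for the same subject on the same day. A site that restores the dose follows Section 6.7 and, on the plain words, breaks Section 6.5. A site that does not restore it does the reverse. Section 10.1.9 allows no deviation except for an immediate hazard, and it lists dosing among the deviations to be notified within 24 hours. The conflict could therefore produce different doses for like subjects at different sites, and deviation reports whichever choice is made.

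The target dose in Section 6.7 raises a second difficulty. It is fixed by what the subject took before the inhibitor, with no allowance for toxicity in between. Section 2.1.2 describes dose-dependent aminotransferase elevation and Section 2.3 describes hepatotoxicity that may be fatal, so the dose after an event should not depend on which section a site reads first.

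**Working it through.** The plan gives no figure to reproduce here. The check compares the sections and uses simple arithmetic on Table 6.5.

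**Step 1: is the 6.7 instruction an increase?** Inputs are the planned and modified total daily doses in Table 6.5.

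| Planned dose (mg/day) | Dose on inhibitor (mg/day) | Increase ordered by 6.7 | Share of planned dose if the ban is applied |
|---|---|---|---|
| 800 | 400 | 800/400 = 2.0-fold | 400/800 = 50% |
| 600 | 400 | 600/400 = 1.5-fold | 400/600 = 67% |
| 400 | 200 | 400/200 = 2.0-fold | 200/400 = 50% |

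Every row is a dose increase in the ordinary sense of the word that Section 6.5 uses. The last column is what the subject would keep receiving after the inhibitor has gone if a site applied the ban literally.

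**Step 2: do the bans contain a limit that removes the conflict?** Two limits could be read into them.
- *Escalation means going above the dose at the end of the prior study.* The layout of Table 6.1 supports this, but neither Table 6.1 nor Section 4.1.3 says it. It would also not cover a subject who left the prior study on a dose already lowered for an inhibitor. Table 6.1 makes that lowered dose the starting level, so restoration would exceed it. The documents do not show whether any such subject exists.
- *The Section 6.5 sentence concerns toxicity only.* It does stand in a paragraph about toxicity, but it is unqualified. The same section uses a toxicity-specific wording elsewhere ("Once dose reduction takes place for toxicity, a dose re-escalation is not allowed"), so the narrower form was available.

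Both limits are plausible and neither is written.

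**Step 3: toxicity while on the inhibitor.** Section 6.7 sets the target as the pre-inhibitor dose without condition. Section 6.5 makes a toxicity reduction permanent. If a reduction for toxicity is made between the start and the end of the inhibitor, literal use of Section 6.7 returns the subject to the full earlier dose, which Section 6.5 rules out. Section 6.7 does not refer the reader to that rule.

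**Step 4: effect on the analysis.** The primary endpoint (Section 9.5.1.1) is the Kaplan-Meier proportion still treatment-free. Its events are resumption of pexidartinib, death, subsequent systemic therapy, or surgery for the tumor. Dose level does not enter, so the estimate is unchanged. The tumor and patient-reported summaries are descriptive (Sections 9.1 and 9.5.1.2).

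**The case against.** The best defense is that Section 6.7 is the specific rule. It names the trigger, the waiting time and the target dose, and a specific rule is normally read as governing over a general one. Returning to a dose that Table 6.5 itself calls planned is not naturally an escalation. Most of this stands, and Section 6.7 is probably what the sponsor intends. It does not remove the need for a sentence saying so, because Section 6.5 bans increases outright.

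A reader might go further and infer that a subject with a liver event on an inhibitor would go back to full dose unguarded. The documents do not support that. Section 6.5 bars re-escalation after a toxicity reduction, Section 2.3 requires discussion with the Medical Monitor before re-challenge, and Table 6.4 and its footnote bring the Medical Monitor into any hold or restart for liver tests.

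A reader might also infer that the dosing tables break down when toxicity occurs on an inhibitor that must be kept. Planned doses of 800 and 600 mg both map to 400 mg, so a Table 6.2 step counted from 800 mg would change nothing. This is too strong as well. Section 6.5 calls the Table 6.3 parameters a guide that does not override clinical judgment, and subjects who cannot tolerate 200 mg twice daily are to be discontinued. Which dose the Table 6.2 steps count from is at most a point for the sponsor's medical team to clarify.

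**Conclusion.** The protocol is inconsistent as written, and it should be corrected. The contradiction is between an ordered increase (Section 6.7) and unqualified bans (Sections 4.1.3, 6.1 and 6.5). A related fault is that the 6.7 target takes no account of toxicity reductions.

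The consequence of applying the ban literally is 50% to 67% of the planned daily dose, by Table 6.5 alone. The consequence of applying Section 6.7 literally is a return to the earlier dose despite a reduction that should be permanent, although the Section 6.5 rules and Medical Monitor review should stop this in practice.

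The documents do not say how many subjects would meet this situation. It is probably few, because Sections 2.3 and 6.7 tell sites to avoid strong inhibitors. The conclusion rests on the protocol text; Section 6.5 refers to a Study Manual and an Investigator's Brochure that are not available here. This is a matter of dosing consistency and safety. It gives no reason to doubt the primary estimate.

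**What to change.** Change the wording in four places.

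- **Section 4.1.3, Table 6.1 and Section 6.5 (after Table 6.4):** add to each ban *except return to the pre-inhibitor dose under Section 6.7, which is not an escalation*. This also covers a subject who entered on a dose already lowered for an inhibitor.
- **Section 6.7:** keep the target "to the dose that was used before starting the inhibitor" and add *less any reduction made for toxicity (Section 6.5; no re-escalation after a toxicity reduction), with any restart after a liver event agreed with the Medical Monitor*.

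No new dose step is proposed. If the sponsor's medical team wishes to state which dose the Table 6.2 steps count from when toxicity occurs on an inhibitor, the statement should be consistent with the 200 mg twice daily floor in Section 6.5.

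The cost is protocol wording only, with no extra patients, visits or data.

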6.7.1. Hormonal Contraceptives

Pexidartinib has been indicated to be a moderate CYP3A4 inducer, as concurrent administration of pexidartinib decreased the AUC_{inf} of the CYP3A4 substrate midazolam by 57%. As the hormonal contraceptive ethinyl estradiol is a CYP3A4 substrate, there is a potential that exposure of ethinyl estradiol may decrease on concurrent administration with pexidartinib. As pexidartinib may cause embryo-fetal harm when administered to a pregnant woman, females of reproductive potential should be advised to use an effective, non-hormonal method of contraception during treatment with pexidartinib and for 1 month after the last dose. Males with female partners of reproductive potential should be advised to use an effective method of contraception during treatment with pexidartinib and for 1 month after the last dose. Female partners of male patients should concurrently use effective contraceptive methods (hormonal or non-hormonal).

6.7.2. Acid-reducing Agents

Avoid the concomitant use of proton pump inhibitors (PPIs) while taking pexidartinib. As an alternative to a PPI, administer pexidartinib 2 hours before or 2 hours after taking a locally-acting antacid, or if using a histamine 2 (H2)-receptor antagonist, administer pexidartinib at least 2 hours before or 10 hours after taking an H2-receptor antagonist.

Permitted Therapies/Products

Subjects are permitted to receive prophylactic or supportive treatment as standard of care during treatment, per Investigator's discretion and institutional guidelines.

- Palliative radiation to non-measurable lesion is permitted as long as the radiation field does not include measurable lesion;
- Investigators' discretion is recommended for the following:
 - Prophylactic or supportive treatment for expected toxicities, including management of study drug will be as per Investigator's discretion.

7. STUDY DRUG DISCONTINUATION AND DISCONTINUATION FROM THE STUDY

This section describes subjects who discontinue pexidartinib treatment as part of this study for reasons listed below and **NOT** subjects who are participating in the Treatment-Free period of the **Treatment-Free/Re-Treatment Cohort**.

7.1. Subject Withdrawal/Discontinuation from the Study

Subjects may discontinue from the study for any of the following reasons:

- Completed
- Complete Response
- Death
- Adverse Event
- Progressive Disease
- Clinical Progression
- Lack of Efficacy
- Withdrawal by Subject (to discontinue study drug)
- Physician Decision
- Lost to Follow-up (see Section [7.2](#) for details on when a subject is considered Lost to Follow-up)
- Pregnancy
- Protocol Deviation
- Study Termination by Sponsor
- Other

If the reason for study discontinuation is the death of the subject, the options for categorizing the primary cause of death are progressive disease or adverse event. If reason of death is unknown, every effort should be made to obtain the primary cause of death. Only 1 AE will be recognized as the primary cause of death.

Only subjects who refuse all of the following methods of follow-up will be considered to have withdrawn consent from study participation (i.e., from the interventional portion and follow-up):

- Attendance at study visits per protocol
- Study personnel contacting the subject by telephone
- Study personnel contacting an alternative person
- Study personnel accessing and reviewing the subject's medical information from alternative sources

If the subject refuses all of the above methods of follow-up, the Investigator should personally speak to the subject to ensure the subject understands all of the potential methods of follow-up. If the subject continues to refuse all potential methods of follow up, the Investigator will document this as a withdrawal of consent (from the interventional portion and follow-up).

Withdrawal Procedures

If a subject is withdrawn from the study:

- The Investigator will complete and report the observations as thoroughly as possible up to the date of withdrawal including the date of last dose, date of last contact, and the reason for withdrawal;
- If disclosure of future information is also withdrawn, the Sponsor may retain and continue to use any data collected before such a withdrawal of consent;
- The subject may request destruction of any samples taken and not tested, and the Investigator must document this in the site study records;
- Study site personnel may use local, regional, and national public records (in accordance with local law) to monitor vital status.

See Schedule of Events (Section 1.3) for data to be collected at the time of study discontinuation and for any further evaluations that need to be completed.

7.2. Lost to Follow-up

A subject will be considered lost to follow-up if he/she fails to return for scheduled visits and is unable to be contacted by the study site staff. Before a subject is deemed lost to follow-up, the Investigator or designee will make every effort to regain contact with the subject (where possible, multiple telephone calls, texts, emails, and if necessary, a certified letter to the subject's last known mailing address or local equivalent methods). These contact attempts should be documented.

If direct contact with the subject is not possible, site personnel must make every effort to collect survival status from public records (e.g., obituaries, death certificates, etc.) in accordance with local laws.

8. STUDY PROCEDURES

See Schedule of Events (Section 1.3) for Screening, Baseline, Treatment, and EOS/EOT Follow-up study procedures.

8.1. Eligibility Assessment

Review the subject's demographics, medical and target disease history (if permitted via the subjects signed ICF, these may be transferred from their prior study records), vital signs, and results of tests (e.g., physical examination, ECG, laboratory assessments) and compare against the eligibility criteria (Section 5.1 and Section 5.2).

Informed Consent

Before a subject's participation in the study, it is the Investigator's responsibility to obtain freely given consent in writing from the subject after adequate explanation of the aims, methods, anticipated benefits, and potential hazards of the study and before any protocol-specific procedures or any study drugs are administered. Subjects should be given the opportunity to ask questions and receive responses to their inquiries and should have adequate time to decide whether or not to participate in the study. The written ICF should be prepared in the local language(s) of the potential subject population. See Section 10.1.2 for additional details.

Tenosynovial Giant Cell Tumor History

Subject's TGCT history will be obtained by the Investigator or a qualified designee. This may be obtained from the subject's file from the prior study.

General Medical History and Baseline Conditions

Subject's medical history will be obtained by the Investigator or a qualified designee.

This may be obtained from the subject's file from the prior study (e.g., the concomitant medications taken during the course of the preceding study will be recorded under prior medications in PL3397-A-U4003). Untoward medical occurrences (including clinically relevant laboratory values that are not symptoms of TGCT/vital signs that are out of range) that were diagnosed or known to exist prior to the consent date will be recorded on the General Medical History and Baseline Conditions eCRF, not the Adverse Event eCRF. Record the start date of any medical occurrence that started before the ICF was signed and is ongoing at the time of the first dose of pexidartinib on the General Medical History and Baseline Conditions eCRF.

Demographics

Review the subject's demographics; which, if permitted via the subjects signed ICF, may be transferred from the subject's file from their prior study, against the eligibility criteria.

